ACTH: adrenocorticotropic hormone; ADA: anti-drug antibody(ies); AFP: alpha-fetoprotein; C: cycle; CA-125: cancer antigen 125; CR: complete response; CT: computed tomography; D: day; disc: discontinuation; DLT: dose-limiting toxicity; ECG: electrocardiogram; ECOG: Eastern Cooperative Oncology Group; F/U: follow-up; FFPE: formalin-fixed paraffin-embedded; HCC: hepatocellular carcinoma; IV: intravenous; MRI: magnetic resonance imaging; NYHA: New York Heart Association; PGx: pharmacogenomics; PK: pharmacokinetic(s); PR: partial response; Q: every; RECIST: Response Evaluation Criteria in Solid Tumors Version 1.1; SD: stable disease; T4: thyroxine; TSH: thyroid stimulating hormone; W: week.

- a. All prior cancer treatments collected as part of medical history.
- b. Biomarker assessment will be performed on the most recent FFPE biopsy of a tumor lesion, preferably collected after progression on the last therapy and/or collected at screening, if clinically feasible. If a recent biopsy is not available, an archival FFPE sample should be provided from a site not previously irradiated. An optional tumor biopsy will be collected at Cycle 3, Day 1 (-3/+1 day), if clinically feasible, to assess pharmacodynamic effects of the drug.
- ^c 12-lead ECG to be recorded at screening (within 7 d of first treatment dose) any time during visit as long as within protocol window. Day 1 of Cycles 1 and 2 to be recorded 1 h ± 30 min following flush of infusion line. Other ECGs to be ordered as clinically indicated by treating physician.
- d. Disease response assessments by RECIST to be performed at Study Week 6, Week 12 and Q6w for subjects assigned to 3- or 6-w treatment schedule, or Q12w for subjects assigned to 12-w treatment schedule until off-disease response evaluation criteria are met.

Confidential Page 49 of 78

- e. AGEN1884 to be administered IV over 60 (-10/+20) min. Subjects with SD, PR, or CR at 12-w evaluation timepoint may continue receiving AGEN1884 every 3, 6, or 12 w (± 7 d) beginning at Study Week 12 for ≤1 year provided they are tolerating study drug. The appropriate schedule will be based on discussion with medical monitor to confirm that proposed schedule is in subject's best interest.

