5.8.6.2 Recording and Reporting

5.8.6.2.1 Adverse Events

Subjects will be assessed for any AEs (non-serious or serious) from the date of consent until 90 days after the last study treatment. Any non-serious AEs identified during this time period will be followed until resolution or stabilization or only until the discontinuation from the study evaluation period if the event is not resolved at the conclusion of the study. The dates of onset and resolution for each AE will be recorded in the subject file. All AEs will be evaluated for duration, intensity, and attribution (relationship) to the investigational agent(s). All AEs (serious and non-serious) and laboratory abnormalities should be assessed for significance by the investigator, with consideration for the subject's overall medical history and concomitant medication profile.

If there is a change from baseline in a laboratory value, physical examination finding, vital sign, or medical finding, and the change is considered by the investigator to be clinically significant, the event must be recorded as an AE.

All AEs regardless of causality or seriousness must be recorded on the electronic case report form (eCRF). The frequency, grade, and nature of irAEs must be recorded.

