6.5 Analysis Visit Window

Data will be analyzed by scheduled visits, where appropriate. Data collected out of the prescribed timing window will be analyzed as scheduled (i.e., at intended visits). Data that are collected from an unscheduled visit will not be included in the by-visit summary tables but will be presented in the listings. However, data collected at an unscheduled visit will also be considered for toxicity grading, in particular, for laboratory assessments. Additionally, both unscheduled and out of window imaging assessments will be included in the efficacy analysis.

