8.6.4 Clinical Laboratory Tests

For clinical laboratory parameters, descriptive summary tables for observed values and changes from baseline will be provided by visit.

Laboratory values will also be categorized according to their NCI-CTCAE version 5 toxicity grade, for the following parameters: ALT, AST, Bilirubin, Creatinine, Hemoglobin, Platelets, Neutrophils, and Lymphocytes. For applicable parameters, shift tables will be presented from the baseline toxicity grade to the worst post-baseline visit value (scheduled or unscheduled). All test results and associated normal ranges from local laboratories will be reported in SI units. All tests with numeric values will have a unique unit per test. Any laboratory test results and associated normal ranges from local laboratories will be converted to SI units. For the limited number of cases where the associated normal ranges from a local laboratory cannot be obtained despite due diligence, if query is unsuccessful at resolving issue and analysis is mandatory then the clinical scientist and medical monitor can provide a suitable normal range to be used in determining CTC grading and flags for above and below normal and the inferred normal range will be flagged in listings.

If a test value is reported with "<" or ">" sign (as below or above some detection limit), the test value will be imputed in summaries at the limit of detection (that is ignoring "<" or ">" signs), however the measurement will be listed as originally reported.

A standard 'eDISH' (evaluation of Drug-Induced Serious Hepatotoxicity) plot will be presented to display on the log-log scale the correlation between peak total bilirubin and alanine aminotransferase (ALT), both in multiples of ULN, with horizontal and vertical lines for Hy's law thresholds, i.e., 3×ULN for ALT and 2×ULN for total bilirubin.

Listing will be provided for Safety Analysis Set.

Confidential Page 25 of 30

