8.6.5 Body Weight and Vital Signs

The observed value and percentage of changes from baseline will be summarized and listed by visit for Safety Analysis Set. If there are multiple measurements per visit, these measurements will be averaged.

Mean values of body weight, with 95% confidence interval will be plotted by each scheduled visit.

Listing will be provided for Safety Analysis Set.

8.6.6 12-lead Electrocardiogram

Number of subjects with abnormal clinically not significant and abnormal clinically significant electrocardiogram (ECG) results, as well as number of subjects with QTc_F (QT interval corrected using Fridericia's formula) greater than 450 or 480milliseconds will be summarized by visit and timing with respect to drug dose. In addition, QTc_F changes from pre-dose will be summarized for number of patients with a change exceeding a threshold of 30 msec or 60 msec. In these summaries, QTc intervals will be averaged for ECG taken in triplicate.

Other ECG parameters will be reported and summarized. Hart rate (HR) will be summarized as for number of patients \leq 50 bpm and \geq 120 bpm, PR interval for number of patients with PR \geq 220 msec, and duration of QRS complex for number of patients with QRS \geq 120 msec.

In all these summaries, QT, PR, QRS durations, and HR will be averaged for ECG taken in triplicate.

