8.6.8 ECOG Performance Status

Shift from baseline ECOG to worst on-study ECOG will be summarized. Listing will be provided for Safety Analysis Set.

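### The by-visit ECG counts in SAP 8.6.6 leave out QTcF exceedances and abnormal tracings found only at unscheduled visits, and no ECG is scheduled at any dosing visit after Cycle 2 Day 1

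*SAP*

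**What the plan says.** SAP 8.6.6 counts subjects with abnormal ECGs (clinically significant or not) and subjects with QTcF above 450 or 480 ms. These counts "will be summarized by visit and timing with respect to drug dose". A further sentence says that QTcF "changes from pre-dose will be summarized for number of patients with a change exceeding a threshold of 30 msec or 60 msec". Heart rate, PR and QRS are also given as numbers of patients beyond stated limits. The section defines no worst post-baseline or any-time count.

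SAP 6.5 sets the general rule: "Data that are collected from an unscheduled visit will not be included in the by-visit summary tables but will be presented in the listings". Its exceptions are toxicity grading, with laboratory tests singled out, and imaging used for efficacy.

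For the ECG schedule, footnote c of Protocol Table 10 covers the dosing visits: "Day 1 of Cycles 1 and 2 to be recorded 1 h ± 30 min following flush of infusion line". It then adds: "Other ECGs to be ordered as clinically indicated by treating physician".

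Two other safety measures in the same SAP are handled differently. For laboratory grades (8.6.4), "shift tables will be presented from the baseline toxicity grade to the worst post-baseline visit value (scheduled or unscheduled" is the wording. For performance status (8.6.8): "Shift from baseline ECOG to worst on-study ECOG will be summarized".

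**The concern.** Change in ECG is a named part of the primary safety endpoint (Protocol 6.2.1.1, SAP 4.4). QTcF above 450 or 480 ms is a fixed numeric threshold, so a subject who crosses it should be counted whatever the investigator thinks of the tracing.

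After Cycle 2 Day 1, any ECG taken during the dosing period is outside the schedule. If it is taken at an unscheduled visit, SAP 6.5 removes it from the table that 8.6.6 produces. The ECG tables could then understate these counts for the part of treatment in which clinically indicated tracings are the main ECG evidence.

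That part of treatment matters. Protocol 3.1 expects some immune toxicity later than Day 42, Protocol 4.3 lists cardiomyopathy among possible immune-related events, and the immune-related clusters in SAP 8.6.2 include myocarditis.

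**Working it through.** The plan states no figure for this point, so the check is a reading of the texts together followed by a count of visits.

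**Step 1: where ECGs are scheduled.** In Table 10 the dosing columns are Cycle 1 Day 1, Cycle 2 Day 1, Cycle 3 Day 1, Cycle 4 Day 1 and the repeating column after Week 12. The ECG row is marked at screening, at the first two dosing columns, and at the three post-treatment columns (after discontinuation, and 28 and 90 days after the last dose). It is blank at the other dosing columns. Footnote c agrees.

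**Step 2: which rule governs each count.**

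| Measure | Tabulation | Unscheduled data |
|---|---|---|
| Abnormal ECG; QTcF >450/>480 ms (SAP 8.6.6) | By visit | Left out under SAP 6.5 |
| QTcF change >30/>60 ms; HR, PR, QRS limits (SAP 8.6.6) | Number of patients | Not stated |
| Laboratory toxicity grade (SAP 8.6.4) | Worst post-baseline | Included |
| ECOG (SAP 8.6.8) | Worst on-study | Worst value used |

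The toxicity-grading exception in 6.5 does not rescue the first row. Section 8.6.6 grades nothing, and every parameter graded in 8.6.4 is a laboratory test.

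**Step 3: dosing visits without a scheduled ECG.** Assume on-time doses on Days 1, 22, 43 and 64, then from Day 85 to no later than Day 365 (Protocol 4.1.1 allows one year at most).

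- Every 3 weeks: (365 − 85)/21 = 13.3, so 14 further doses. Total 18, last on 85 + 13 × 21 = Day 358.
- Every 6 weeks: 280/42 = 6.7, so 7 further doses. Total 11, last on 85 + 6 × 42 = Day 337.
- Every 12 weeks: 280/84 = 3.3, so 4 further doses. Total 8, last on 85 + 3 × 84 = Day 337.

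Two dosing visits carry a scheduled ECG in every case.

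| Schedule | Doses | Without scheduled ECG | Days from the Day 22 ECG to last dose |
|---|---|---|---|
| Every 3 weeks | 18 | 16 (88.9%) | 358 − 22 = 336 |
| Every 6 weeks | 11 | 9 (81.8%) | 337 − 22 = 315 |
| Every 12 weeks | 8 | 6 (75.0%) | 337 − 22 = 315 |
| Stops after 4 doses | 4 | 2 (50.0%) | 64 − 22 = 42 |

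**Step 4: illustration of the undercount.** The documents give no rate for such findings. If 1 to 5 of 60 Phase 2 subjects had one only at an unscheduled visit in this interval, the by-visit table would miss 1/60 = 1.7% to 5/60 = 8.3% of subjects.

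**The case against.** - **Adverse event reporting.** Protocol 5.8.6.2.1 says that where there is a change from baseline and "the change is considered by the investigator to be clinically significant, the event must be recorded as an AE". Those findings should appear in the TEAE tables. This stands and narrows the gap to threshold crossings and to abnormalities judged not clinically significant. It does not close the gap, because that route depends on judgement and the threshold does not.
- **Unscheduled visit versus unscheduled test.** SAP 6.5 excludes data from unscheduled visits. A clinically indicated ECG taken at, say, Cycle 3 Day 1 might still be tabulated. This also stands: the fractions in Step 3 describe how sparse the schedule is and do not measure how many findings are lost.
- **Persistence and exposure.** Scheduled post-treatment ECGs enter the table, so a finding that lasts until then is counted. One year is the maximum treatment, and after four doses the interval is only 42 days. Both points limit the size.
- **Other 8.6.6 counts.** QTcF change, heart rate, PR and QRS are not said to be by visit, so they may already include unscheduled tracings. The SAP is silent, and one sentence would settle it.
- **Consistency.** Vital signs are also summarised by visit with no worst-value rule, and Protocol 6.4.1 does not list ECG among the safety parameters. Neither justifies undercounting a numeric threshold within the primary safety endpoint.
- **Consequence.** The study is single-arm and descriptive, no Phase 2 decision rule uses ECG counts, and the tracings remain in listings. Keeping symptom-triggered ECGs apart is defensible, but labelled extra rows do that as well. The listing itself rests on 6.5 alone, since 8.6.6 names none.

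**Conclusion.** The concern holds. As written, a QTcF value above 450 or 480 ms, or an abnormality judged not clinically significant, that is found only at an unscheduled visit is left out of the SAP 8.6.6 by-visit counts. No AE record is required for it unless the investigator judges the change clinically significant.

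The exposed interval runs from Day 22 to the last dose: 42 days for a four-dose subject and 315 to 336 days over a full year, assuming on-time dosing. The number of subjects affected cannot be derived from the documents, and the 1.7% to 8.3% is an assumed illustration. The study's conclusions are not invalidated, but a component of the primary safety endpoint can be understated, so the SAP should be changed.

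**What to change.** Add to SAP 8.6.6 a per-subject worst post-baseline summary that uses scheduled and unscheduled ECGs:

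- worst abnormality category;
- maximum QTcF against 450 and 480 ms;
- maximum QTcF change from the SAP 6.1 baseline against 30 and 60 ms;
- the heart rate, PR and QRS limits already stated.

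Keep the by-visit table, and label the new rows as including unscheduled tracings. This applies the rule that SAP 8.6.4 already uses for laboratory grades and removes the doubt about the counts not described as by visit.

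The cost is one SAP sentence and a few table rows, with no new ECGs. The drawback is that the counts will include ECGs prompted by symptoms, which the label discloses.

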- c. Subjects enrolling in Phase 2 must have cancer that has progressed after prior treatment with an approved or investigational PD-1/PD-L1 inhibitor as their most recent therapy (2-6 weeks prior to first dose of study drug). The minimum requirement of 2 weeks (14 days) from prior anti−PD-1/PD-L1 therapy is to allow resolution of any lower-grade (≤2) adverse events observed with the therapy. If the investigator feels the subject has tolerated prior anti−PD-1/PD-L1 therapy well, then treatment with study agent may begin sooner.
- d. \leq 7 days for prior corticosteroid treatment, with the following exceptions:
 - Use of an inhaled or topical corticosteroid is permitted.
 - Corticosteroid premedication for radiographic imaging for dye allergies is permitted.
 - Use of physiologic corticosteroid replacement therapy may be approved after consultation with the medical monitor.

Confidential Page 30 of 78

- e. \leq 21 days for prior monoclonal antibody used for anticancer therapy, with the exception of denosumab. This does not apply to subjects being enrolled in Phase 2, who have received a PD-1/PD-L1 inhibitor as their most recent therapy (2-6 weeks prior to first dose of study drug; see above).
- f. \leq 7 days for immunosuppressive-based treatment for any reason, with the exceptions noted above for prior corticosteroid treatment (exclusion criterion d).
- g. \leq 21 days or 5 half-lives before first dose of study treatment for all other investigational study drugs or devices. For investigational agents with long half-lives (e.g., >5 days), enrollment before the fifth half-life requires medical monitor approval.
- h. For subjects in Phase 2 with HCC < 6 weeks for prior locoregional therapy to the liver e.g., transcatheter chemoembolization (TACE), radiation, surgery, or radioembolization.
- 8. Has not recovered to grade ≤1 from toxic effects of prior therapy and/or complications from prior surgical intervention before starting therapy.
 - **Note**: Subjects with grade ≤ 2 neuropathy and alopecia are an exception and may enroll.
- 9. Uncontrolled infection or other serious medical illnesses.
- 10. History or presence of an abnormal ECG that, in the investigator's opinion, is clinically meaningful.
- 11. Any medical conditions that, in the opinion of the investigator, would preclude use of AGEN1884, including AGEN1884 hypersensitivity.
- 12. Women who are pregnant or breastfeeding.
- 13. Concurrent participation in other investigational drug trials.

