- Other AEs of special interest determined by investigators

Unless otherwise stated, the number of subjects with an event (subject-wise) and the number of events (event-wise) will be provided for each summary.

Immune-related AEs will be tabulated using investigator-reported irAEs.

Confidential Page 21 of 30

Agenus Inc. Statistical Analysis Plan for Study C-500-01 Phase 2

Infusion related AEs will be tabulated using infusion-related reactions as reported by the investigators.

The following summaries by either SOC and PT or by PT and by severity grade will be provided. Summaries will be sorted by decreasing incidence of PT (within SOC, if applicable).

- TEAEs by SOC and PT, and by PT
- TEAEs by relationship to study drug, severity grade, SOC, and PT
- Drug-related TEAEs by SOC and PT, and by PT
- TEAEs leading to permanent treatment discontinuation by PT
- TEAEs leading to death by PT
- Drug-related TEAEs leading to permanent treatment discontinuation by PT
- Drug-related TEAEs leading to death by PT
- Serious TEAEs by SOC and PT, and by PT
- Serious TEAEs by relationship to study drug and severity grade, by SOC and PT
- Drug related serious TEAEs by SOC and PT, and by PT
- irAEs by SOC and PT, and by PT
- irAEs by severity grade, SOC, and PT
- Infusion-related TEAEs by SOC and PT, and by PT
- Infusion-related TEAEs by severity grade, SOC, and PT
- Laboratory abnormalities worsening (in at least one on-study measurement, relative to baseline) by NCI-CTCAE version 5 criteria.
- Alanine aminotransferase (ALT), aspartate aminotransferase (AST), or bilirubin normal at baseline but with elevations $\geq 2 \times \text{upper limit of normal (ULN)}$

The overall summary of TEAEs will be reported by age (age < 55 vs age \geq 55, age < 65 vs age \geq 65, and age < 75 vs age \geq 75), by race group including at least 5 subjects (groups with < 5 subjects will be reported summarily as "Other"), by normal vs abnormal creatinine and bilirubin levels at baseline, and by drug manufacturing process. Subgroup analyses will be provided for HCC patients, non-HCC and PD-1/PD-L1 refractory patients, and non-HCC and PD-1/PD-L1 naïve patients.

In addition, the overall summary of AE incidence per month of drug exposure will be presented. Such a summary will report #patients/(total time of exposure in months) and #AEs/(total time of exposure in months.)

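### SAP 8.6.6 counts subjects beyond QTcF, HR, PR and QRS limits without reference to each subject's baseline and plans no ECG shift table, so newly arising abnormalities cannot be told from pre-existing ones within subjects

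*SAP*

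**What the plan says.** SAP 8.6.6 (12-lead Electrocardiogram) sets these displays:

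- **QTcF, absolute:** the number of subjects with values "greater than 450 or 480milliseconds will be summarized by visit and timing with respect to drug dose". Clinically significant and not significant abnormal ECGs are tabulated in the same way.
- **QTcF, change:** "changes from pre-dose will be summarized for number of patients with a change exceeding a threshold of 30 msec or 60 msec".
- **HR:** "will be summarized as for number of patients" at or below 50 bpm and at or above 120 bpm.
- **PR:** "PR interval for number of patients with PR" at or above 220 msec.
- **QRS:** "duration of QRS complex for number of patients with QRS" at or above 120 msec.

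For HR, PR and QRS the section names no visit, timing, change or shift.

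SAP 6.1 makes the last non-missing value before first dose the baseline for all evaluations unless otherwise noted. SAP 4.4 includes changes in ECG in the primary safety assessment.

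The protocol schedules a screening ECG within 7 days before first dose (section 5.1.1 and Table 10, footnote c). For dosing days, footnote c reads "Day 1 of Cycles 1 and 2 to be recorded 1 h ± 30 min following flush of infusion line". On eligibility, exclusion 10 in Protocol 3.2.2 begins "History or presence of an abnormal ECG that" and applies only where the investigator considers the abnormality clinically meaningful. No HR or interval limit appears in the entry criteria.

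**The concern.** A subject can enter with a wide QRS, a long PR or a slow rate that the investigator regards as unimportant. If that finding simply persists, the subject meets the 8.6.6 criterion at every visit. The table then records an abnormality that treatment did not cause, and nothing in it marks the abnormality as old.

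There is no control arm (SAP 3.3) whose background rate could be set against this, so each subject's own baseline is the only comparator available. The primary safety endpoint refers to change in ECG, and a bare count above a limit does not measure change. The gap is widest for PR and QRS, which have no change analysis in any section.

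A smaller point concerns the QTcF change analysis. Its reference is called *pre-dose*, a term 8.6.6 does not define. One programmer could take it as the SAP 6.1 baseline. Another could look for an ECG before the infusion at the same visit, which is not scheduled.

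**Working it through.** The plan gives no ECG rate, power or sample-size figure, so there is nothing to reproduce. The check sets the provisions side by side and then illustrates scale.

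**1. What each parameter gets**

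| Parameter | Limit in 8.6.6 | Conditioned on baseline | Change or shift analysis |
|---|---|---|---|
| QTcF | > 450, > 480 msec | No | Change > 30, > 60 msec from *pre-dose* |
| HR | ≤ 50, ≥ 120 bpm | No | None in 8.6.6; pulse, as a vital sign, gets percentage change from baseline in 8.6.5 |
| PR | ≥ 220 msec | No | None |
| QRS | ≥ 120 msec | No | None |

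Baseline-conditioned limit counts: 0 of 4. Parameters with an explicit change analysis in 8.6.6: 1 of 4.

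**2. What the SAP does elsewhere**

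SAP 8.6.2 lists ALT, AST or bilirubin "normal at baseline but with elevations" of at least 2 × ULN. SAP 8.6.4 plans shift tables from baseline grade to worst post-baseline value for applicable laboratory parameters. SAP 8.6.8 plans a shift from baseline to worst ECOG.

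**3. Which ECGs are available as a reference**

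- Scheduled before first dose: 1 (screening).
- Scheduled on a dosing day before the infusion: 0.
- Scheduled on a dosing day after the infusion: 2 (Day 1 of Cycles 1 and 2).

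The screening ECG precedes both post-infusion ECGs and is the baseline under SAP 6.1, so a change can be calculated for each.

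**4. What a by-visit table can and cannot show**

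Suppose *a* of *N* subjects are beyond a limit at screening and *b* at a later visit, all with both ECGs. The number newly beyond the limit lies between max(0, *b* − *a*) and min(*b*, *N* − *a*). With *N* = 60 and *a* = *b* = 3:

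- lower bound: max(0, 3 − 3) = 0
- upper bound: min(3, 60 − 3) = 3

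The same table fits no new abnormality (the same three subjects) and three new ones (three different subjects). Only a within-subject cross-tabulation separates these.

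**5. Illustration of scale**

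*N* = 60 is the Phase 2 maximum in SAP 3.2. The share *p* already beyond a given limit at entry is assumed, since the documents give no prevalence. With no drug effect and no measurement change:

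- expected count = *N* × *p*
- chance of at least one = 1 − (1 − *p*)^*N*

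| *p* (assumed) | Expected count | Chance of at least one |
|---|---|---|
| 2% | 60 × 0.02 = 1.2 | 1 − 0.98^60 = 70% |
| 5% | 60 × 0.05 = 3.0 | 1 − 0.95^60 = 95% |
| 10% | 60 × 0.10 = 6.0 | 1 − 0.90^60 = 99.8% |

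For 40 subjects the expected counts are 0.8, 2.0 and 4.0. A newly-beyond-limit count would be 0 under the same assumptions. In practice some subjects close to a limit will cross it through measurement variation alone, and a shift table does not remove that.

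**The case against.** Several arguments favour the plan.

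- **Display by visit.** QTcF and the normal/abnormal counts are tabulated by visit and timing, and SAP 6.5 makes analysis by scheduled visit the general rule where appropriate. A screening row can therefore stand beside later rows. This holds at group level. It does not identify newly abnormal subjects, and for HR, PR and QRS section 8.6.6 does not itself call for the by-visit layout.
- **Adverse event route.** Under Protocol 5.8.6 an ECG change judged clinically significant is recorded as an AE, and SAP 8.6.2 requires TEAEs to have onset, or worsening of a pre-existing condition, after dosing starts. This also stands. Clinically important new findings are captured elsewhere, so a reader who inferred that the plan cannot detect any new ECG abnormality would be wrong. The route depends on investigator judgement and does not make the interval counts interpretable.
- **Mixed methods elsewhere.** The eDISH plot in SAP 8.6.4 uses peak values with no baseline condition. Absolute-limit displays are thus not foreign to the SAP, but laboratory data have a shift table as well and ECG data do not.
- **The QTcF reference.** Because no dosing-day pre-infusion ECG is scheduled, a reader might infer that the QTcF change analysis has no reference value. The documents do not support this. Section 8.6.6 does not ask for a same-day ECG, and the screening ECG is available as the SAP 6.1 baseline. The fault is an undefined term, not a missing ECG.
- **Descriptive tables only.** No decision rule, sample size or error rate depends on these counts. That is correct and limits the weight of the point.

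**Conclusion.** The point holds as a gap in the safety display. None of the four sets of limit counts refers to baseline, no ECG shift is planned, and PR and QRS have no change analysis at all. HR is partly covered through pulse in 8.6.5, and QTcF has a workable change analysis once *pre-dose* is defined.

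A reader might go further and infer that pre-existing abnormalities will be reported as on-treatment findings. That is a risk, greatest for PR and QRS, and not a certainty: a by-visit layout may show the screening background.

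The illustrative size is 1.2 to 6 subjects of 60 counted per limit with no drug effect. It rests wholly on the assumed 2% to 10% entry prevalence and should not be read as an estimate for this trial. The textual finding does not depend on it. The change is worth making because it concerns part of the primary safety endpoint, follows the SAP's own approach for laboratory grades and ECOG, and uses ECGs already collected.

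**What to change.** In SAP 8.6.6:

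1. Define *pre-dose* in the QTcF change analysis as the SAP 6.1 baseline, which under the protocol schedule is normally the screening ECG.
2. For QTcF, HR, PR and QRS, add a table of baseline category against worst post-baseline category, using the limits already stated; treat low and high HR separately. Alternatively, count subjects newly beyond each limit and give a separate line for those already beyond it at baseline. That line is needed because a count restricted to subjects within limits at baseline would hide worsening in the others.
3. Keep the by-visit and timing display. It separates screening from post-infusion ECGs. State that it applies to HR, PR and QRS too.

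No new ECG or visit is needed. The cost is SAP wording, one or a few extra tables and minor programming.
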